## **5.2 Monitoring and Recording an Adverse Event**

**Definition.** Any clinically relevant deterioration in laboratory assessments or other clinical finding is considered an AE.

**Reporting source.** AEs may be spontaneously reported by the patient and/or in response to an open question from study personnel or revealed by observation, physical examination or other diagnostic procedures.

**Prior to the trial.** Planned hospital admissions or surgical procedures for an illness or disease that existed before the patient was enrolled in the trial are not to be considered AEs unless the condition deteriorated in an unexpected manner during the trial (e.g., surgery was performed earlier or later than planned).

**Pretreatment events following signed informed consent.** For serious pretreatment events, the investigator must determine both the intensity of the event and the relationship of the event to study procedures.

**Treatment events.** For serious AEs, the investigator must determine both the intensity of the event and the relationship of the event to study drug administration.

Not serious AEs. For non-serious AEs, the investigator must determine both the intensity of the event and the relationship of the event to study drug administration.

### **Follow-up of Adverse Events**

All adverse events will be followed with appropriate medical management 30 days following the last dose of the study drug or treatment or until they are resolved, if they are related to the study treatment.

#### **5.2.1 Procedure for Reporting Drug Exposure during Pregnancy and Birth Events**

If a woman becomes pregnant, or suspects that she is pregnant, while participating in this study, she must inform the investigator immediately and permanently discontinue the study drug. The sponsor-investigator must notify the DSMC by email. The pregnancy must be followed for the final pregnancy outcome.

If a female partner of a male patient becomes pregnant during the male patient's participation in this study, the sponsor-investigator must also immediately notify the DSMC by email. Every effort should be made to follow the pregnancy for the final pregnancy outcome.

Suggested Pregnancy Reporting Form:

- Pregnancy Report Form (a sample is provided in the appendices)

#### **5.2.2 Subject Complaints**

If a complaint is received by anyone on the study staff, it will be discussed with the study staff and will be addressed on a case-by-case basis. The PI will be notified of any complaints. Complaints will be reported to the IRB if indicated.

If the subject has questions about his or her rights as a study subject, wants to report any problems or complaints, obtain information about the study or offer input, the subject can call the Medical College of Wisconsin/Froedtert Hospital research subject advocate at [contact]. This information is provided to the subject in their consent.

A product complaint is a verbal, written or electronic expression that implies dissatisfaction regarding the identity, strength, purity, quality or stability of a drug product. Individuals who identify a potential product complaint situation should immediately contact the sponsor and report the event. Whenever possible, the associated product should be maintained in accordance with the label instructions pending further guidance from a sponsor representative. Product complaints in and of themselves are not reportable events. If a product complaint results in an SAE, an SAE form should be completed.

### **5.2.3 Routine Reporting Procedures for AEs**

#### *Expedited Reporting Procedures for SAEs, SARs, UPIRSOs and DLTs.*

Since this is an investigator-initiated study, the principal investigator, also referred to as the sponsor-investigator, is responsible for reporting serious adverse events (SAEs) to any regulatory agency and to the sponsor-investigator's IRB. Regardless of expectedness or causality, all SAEs (including serious pretreatment events) must also be reported to the DSMC as soon as possible, but no later than five calendar days of the sponsor-investigator's observation or awareness of the event.

Signs or symptoms reported as adverse events will be graded and recorded by the investigator, according to the CTCAE. When possible, signs and symptoms indicating a common underlying pathology should be noted as one comprehensive event.

The investigator will assess all adverse events and determine reporting requirements to the MCWCC Data and Safety Monitoring Committee (DSMC) and MCW's Institutional Review Board, and, when the study is conducted under an Investigational New Drug Application (IND), to the Food and Drug Administration (FDA), if it meets the FDA reporting criteria. The investigator will report SAEs to any regulatory agency and to the sponsor-investigator's IRB.

All adverse events, whether or not unexpected, and whether or not considered to be associated with the use of the study drug, will be entered into OnCore®.

#### **Reporting to the Data and Safety Monitoring Committee**

Regardless of expectedness or causality, all SAEs (including serious pretreatment events) must also be reported to the DSMC as soon as possible, but no later than five calendar days of the sponsor-investigator's observation or awareness of the event.

**Report Method:** The investigator will use email to report SAEs to the DSMC. The SAE report must include event term(s), serious criteria and the sponsor-investigator's or sub-investigator's determination of both the intensity of the event(s) and the relationship of the event(s) to study drug administration. Intensity for each SAE, including any lab abnormalities, will be determined by using the NCI CTCAE as a guideline whenever possible.

The criteria are available online at <http://ctep.cancer.gov/reporting/ctc.html>.

#### **Reporting to MCW Committee Institutional Review Board**

The principal investigator must report events to the MCW IRB within five business days of his/her awareness of the event.

[Guidance on Adverse Event Reporting to the IRB is available online at [MCW IRB Policies and Procedures.](#)]

#### **Expedited Reporting to the Food and Drug Administration**

If the study is being conducted under an IND, the sponsor-investigator is responsible for determining whether or not the suspected adverse reaction meets the criteria for expedited reporting in accordance with Federal Regulations (21 CFR §312.32).

The investigator must report in an IND safety report any suspected adverse reaction that is both serious and unexpected. The sponsor-investigator needs to ensure that the event meets all three definitions:

- Suspected adverse reaction
- Unexpected
- Serious

If the adverse event does not meet all three of the definitions, it should not be submitted as an expedited IND safety report.

The timeline for submitting an IND safety report to FDA is no later than **15 calendar days** after the investigator determines that the suspected adverse reaction qualifies for reporting (21 CFR 312.32(c)(1)).

Any unexpected fatal or life-threatening suspected adverse reaction will be reported to FDA no later than **seven calendar days** after the investigator's initial receipt of the information (21 CFR 312.32(c)(2)).

Any relevant additional information that pertains to a previously submitted IND safety report will be submitted to FDA as a Follow-up IND Safety Report without delay, as soon as the information is available (21 CFR 312.32(d)(2)).

***Suggested Reporting Form:***

- US FDA MedWatch 3500A:  
<http://www.fda.gov/Safety/MedWatch/HowToReport/DownloadForms/default.htm>

Any other form deemed appropriate by the sponsor-investigator.

Event Type	Report Recipients				
	PI/Study Chair/ Coordinating Center	Institutional Review Board	DSM C	FDA	CTO Regulator y Office
Serious Adverse Event	ASAP	5 days (or annual CPR) 	5 days	7 or 15 days 	ASAP
Unanticipated Problems Involving Risks to Subjects of Others	ASAP	5 days (or annual CPR) 	5 days	7 or 15 days 	ASAP
Evidence of Causal Relationship between Drug and AE	ASAP	5 days (or annual CPR) 	5 days	7 or 15 days 	ASAP
Dose-Limiting Toxicity	ASAP	5 days (or annual CPR) 	5 days	7 or 15 days 	ASAP
Contacts					
Role	Name	Entity/Department	Institution	Telephone	Email
Sponsor-Investigator			MCW	414-	
Research Coordinator			MCW	414-	
IRB Representative			MCW	414-	
DSMC			MCW	414-	
Regulatory Contact			MCW	414-	
FDA			FDA		

#### Footnotes

 Consult MCW IRB Policies (contact your regulatory representative)

 FDA guidelines: Suspected adverse reaction, Unexpected and Serious = 7 Days; If not = 15 days

## 6 STATISTICAL CONSIDERATIONS

Benmiloud et al. studied the impact of NIRAF-based identification of parathyroid glands which comprised of a group of 93 patients where NIRAF was used by a surgeon for parathyroid identification and a control group of 153 patients where NIRAF was not used (19). Their study reported that mean parathyroid glands identified by surgeon with NIRAF imaging was significantly higher at  $3.1 \pm 0.9$ , while that of same surgeon without NIRAF imaging was  $2.6 \pm 0.1$  ( $p=0.0001$ ). Based on this data (mean difference: 0.5 and standard deviation: 1.0), it was determined that in order to observe a statistically significant difference (i.e. for an expected mean difference: 0.7 and expected standard deviation: 1.0), 33 patients would be required per group (for a 95% powered study). Since this study may involve patient follow-up for data up to 6 months after surgery, we will thus assume an approximate data attrition rate of 20%, thus requiring a recruitment of 40 patients per group. Therefore, a total of 80 patients (study and control arm) should be recruited per surgeon for this study at this study site.

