## PROTOCOL SUMMARY

Title	Evaluating Impact of Near Infrared Autofluorescence (NIRAF) Detection for Identifying Parathyroid Glands during Parathyroidectomy
Principal Investigator	[name]
Study Population	Parathyroidectomy patients
Primary Objectives	The specific aim of this study is to determine if PTeye is beneficial or not for (i) intraoperative identification of parathyroid tissues, (ii) improving efficiency of parathyroid surgeries, and (iii) minimizing risk of postsurgical complications.
Study Design	Double-arm, open-label
Study Intervention	PTeye
Number of Subjects	N = 160. Each investigator will enroll 40 subjects to the PTeye group and 40 subjects to the control group.
Estimated Time to Complete Enrollment:	Approximately 2 years

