## **2.3 Secondary Outcome Measures**

### **2.3.1 Overall number of parathyroid glands identified**

Overall number of parathyroid glands identified (Experimental Group: Glands identified with naked eye + NIRAF; Control Group: Glands identified with naked eye) [Time Frame: Immediate. During PTx procedure.]

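### Section 6 claims 95% power from 33 per group for a difference of 0.7 with SD 1.0, but those inputs give about 80% (two-sided 5%) or 88% (one-sided 5%)

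*Combined protocol and SAP*

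**What the plan says.** Section 6 (Statistical Considerations) starts from a cited study of gland identification with and without autofluorescence imaging. It reports means of 3.1 ± 0.9 (93 patients) and 2.6 ± 0.1 (153 patients) with p=0.0001, and summarises these as "Based on this data (mean difference: 0.5 and standard deviation: 1.0"). It then plans on a larger effect, "for an expected mean difference: 0.7 and expected standard deviation: 1.0", and concludes that "33 patients would be required per group (for a 95% powered study").

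An allowance of 20% for attrition follows, "thus requiring a recruitment of 40 patients per group", which makes 80 per surgeon. The Protocol Summary repeats this for a total of 160: "Each investigator will enroll 40 subjects to the PTeye group and 40 subjects to the control group". That total corresponds to two surgeons (160/80 = 2).

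Alpha, sidedness and the test are not given. The text says only that "it was determined that in order to observe a statistically significant difference" this number was needed. The number of glands identified is a secondary outcome (Section 2.3.1), recorded during the operation.

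**The concern.** A standardised difference of 0.7 is too small for 33 per group to give 95% power at any usual 5% test. If the statement is wrong, readers are misled about the risk of missing a real effect. Someone relying on Section 6 would take a null result for one surgeon as carrying a 5% false-negative risk for a difference of 0.7. At conventional levels that risk is two to four times as high with the 33 evaluable patients assumed. Section 6 is the only place where the sample size is justified, and the 40 per group, 80 per surgeon and 160 in total all derive from the figure of 33.

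**Working it through.** **Inputs (Section 6 and Protocol Summary).** Difference δ = 0.7; SD σ = 1.0; 33 per group; stated power 95%; 1:1 allocation; 40 per group recruited. Assumed, because it is not stated: a two-sample t-test at 5%, shown both two-sided and one-sided.

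**Attempt to reproduce 33 at 95% power.** With the normal approximation, n per group = 2σ²(z_alpha + z_power)²/δ².

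- Two-sided 5%, 95% power: 2 × (1.960 + 1.645)²/0.49 = 53.04, so 54. The noncentral t gives 54.02, so 55 if rounded up.
- One-sided 5%, 95% power: 2 × (1.645 + 1.645)²/0.49 = 44.2, so 45. The noncentral t gives 44.87, also 45.
- Two-sided 5%, 80% power: 2 × (1.960 + 0.842)²/0.49 = 32.04, so 33. The noncentral t gives 33.02.

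The printed 33 is therefore what the stated inputs give for 80% power, two-sided, and not for 95%.

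**Power at the stated sizes.** With the normal approximation, power = Φ(δ/(σ√(2/n)) − z_alpha). At n = 33, 0.7/√(2/33) = 2.843. Two-sided: Φ(2.843 − 1.960) = 81.2%. One-sided: Φ(2.843 − 1.645) = 88.5%. The noncentral t values, used from here on, are slightly lower:

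| Difference (SD 1.0) | n per group | Two-sided 5% | One-sided 5% |
|---|---|---|---|
| 0.7 | 33 | 80.0% | 87.9% |
| 0.7 | 40 | 87.1% | 92.8% |
| 0.5 | 40 | 59.8% | 71.6% |

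The difference detectable with 95% power, two-sided, is 0.90 at 33 per group and 0.82 at 40.

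**Could another alpha explain it?** At one-sided 10%, 33 per group gives 93.9% and 95% power still needs 35.4 per group. Exactly 95% at n = 33 would need a two-sided alpha of about 0.23.

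**Could other inputs explain it?** The SDs printed for the cited study pool to √((92 × 0.81 + 152 × 0.01)/244) = 0.558. With a difference of 0.5, n for 95% power is 2 × 0.558² × (1.960 + 1.645)²/0.25 = 32.4, so 33 (33.4 by the noncentral t). This matches, but Section 6 attaches 33 to 0.7 and 1.0 and gives the SD as 1.0 in both places.

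**Side checks.**

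- *Control SD.* Section 6 says "that of same surgeon without NIRAF imaging was" 2.6 with an SD of 0.1. A pooled t-test on the printed means and group sizes gives t = 6.81, p = 7.5 × 10⁻¹¹ with that SD (Welch 6.6 × 10⁻⁷). With a control SD of 1.0 it gives t = 3.95, p = 0.000104, which agrees with the reported 0.0001. This assumes that the cited study used a t-test.
- *All patients.* With 80 per arm, adjustment for surgeon (157 degrees of freedom), the same effect for both surgeons and no losses, two-sided power is 99.3% for 0.7 and 88.2% for 0.5.
- *Attrition.* 33/0.8 = 41.25, so 42. The printed 40 matches 33 × 1.2 = 39.6.

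**The case against.** The arithmetic is hard to contest; the case on the other side is about weight.

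- *Scope.* Gland count is secondary, no per-surgeon test is specified, and the whole trial has good power for it. This stands, and limits the consequence. It does not make the 95% correct, because Section 6 sizes the study per surgeon and attaches the figure to 33 per group.
- *Unstated alpha.* At one-sided 10%, 40 per group would give 96.7%. True, but 10% one-sided is not a conventional level, nothing in the plan suggests it, and 33 per group still falls short of 95% there.
- *Pooled power shown at its best.* With the plan's own 20% attrition (about 64 to 66 per arm), power for a difference of 0.5 falls from 88% to about 80–81%. That is fair as a range, although six-month losses should hardly affect a count made in the operating room.
- *Explanations for the mismatch.* Both the 80% reading and the pooled-SD reading are inference. The documents do not settle which applies, or whether the control SD of 0.1 is a slip. These points are reasons to ask the sponsor and are not part of the error.
- *Attrition rounding.* The 40 against 42 is minor, since the plan calls the rate approximate.

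**Conclusion.** The concern holds. Under a two-sample t-test at 5%, one- or two-sided, a difference of 0.7 with SD 1.0 and 33 per group does not give 95% power. For one surgeon the false-negative risk for that difference is 20% two-sided (12% one-sided) at 33 per group, and 13% (7%) if all 40 are evaluable, against the stated 5%. For the cited difference of 0.5 at 40 per group it is about 40% two-sided.

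Whether the power or the inputs are wrong cannot be told from the documents. The fault is a false power statement in the only sample-size justification. It does not show that the trial is too small for gland count. It also says nothing about power for the primary outcomes in Section 2.2, which this calculation does not address.

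**What to change.** Rewrite the paragraph in Section 6:

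1. State alpha, sidedness and the test.
2. Say which calculation was run, and reconcile n, difference, SD and power. Check the control SD of 0.1 against the cited study.
3. Unless a different calculation was run, replace the 95% with the per-surgeon power at two-sided 5% and SD 1.0: 80% at 33 and 87% at 40 per group for a difference of 0.7, and 60% at 40 per group for 0.5.
4. Preferably, add the power of a surgeon-adjusted comparison of all patients: about 99% for 0.7 and 88% for 0.5 at 80 per arm, assuming a common effect and no losses.
5. Give the reason for planning on 0.7 when the cited data show 0.5, and correct or explain the step from 33 to 40.

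The cost is one paragraph and a less favourable power figure. Restating the power needs no extra patients and no change to recruitment, allocation or procedures.

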# 1 BACKGROUND

## Parathyroid Surgery

Inability of the surgeon to identify or localize the diseased PG can occur in 5 – 10% of cases resulting in failed parathyroidectomies (1, 2). As a result, persistent hyperparathyroidism can occur in these patients resulting in unnecessary repeat surgeries that may be associated with increased morbidity and costs (3, 4). Ultrasound imaging, 99mTechnetium-sestamibi scintigraphy, and computed tomography (CT) have so far demonstrated variable efficacy in preoperative localization of diseased PGs (5, 6) and may not always correlate well with the surgical field of view as observed intraoperatively. Consequently, most surgeons rely on visual identification of PGs during surgery, whereby the accuracy of PG identification is eventually determined by her/his surgical skill and experience (7, 8). When in doubt, a surgeon routinely confirms the identity of PG tissue intraoperatively by sending the specimen for frozen section analysis that typically requires a wait time of 20–30 minutes per sample (9) and has additional costs.

By easily being able to distinguish parathyroid from other tissues intraoperatively, postsurgical complications and associated costs may be reduced. The unique discovery of near infrared autofluorescence (NIRAF) in parathyroid tissues demonstrated that optical modalities that detect NIRAF can be utilized for non-invasive and label-free identification of parathyroid tissues with an accuracy as high as 97%.(10, 11) Since then, several research groups have explored the feasibility of localizing parathyroid glands using NIRAF detection with reasonable success, resulting in FDA approval for this optical technique (12). In this study, we plan to evaluate whether an FDA-approved device called 'PTeye' (AiBiomed, Santa Barbara, CA) is beneficial or not, for the surgeon and patient during parathyroid operations. The results of such a study will help us to understand and assess the true impact of optical modalities such as PTeye on (i) improving the quality and efficiency of parathyroid surgeries and (ii) minimizing risk of postsurgical complications and related expenses.

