### **2.2 Primary Outcome Measures**

#### **2.2.1 Persistent hyperparathyroidism (Immediate)**

Failure of intra-operative parathyroid hormone (PTH) to normalize (defined as failure of PTH to drop > 50% of its baseline value at final intra-operative PTH assay and/or failure of PTH to drop < 65 pg/ml or 6.9 pmol/L). [Time Frame: During parathyroidectomy (PTx) procedure]

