#### **2.2.2 Persistent hyperparathyroidism or hypercalcemia (transient)**

Elevated blood calcium levels (total blood calcium level > 10.5 mg/dL or 2.6 mmol/L) with/without elevated parathyroid hormone (PTH) (serum intact PTH > 65 pg/ml or 6.9 pmol/L) at first postoperative visit. [Time Frame: 5-14 days after PTx procedure]

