### **2.2.3 Persistent hyperparathyroidism or hypercalcemia (failed parathyroidectomy)**

If blood calcium with/without parathyroid hormone (PTH) has not normalized at 1st post-operative visit, calcium and/or PTH is subsequently measured as necessary. Patient is defined to have a failed parathyroidectomy if hypercalcemia/hyperparathyroidism (defined as total blood calcium level > 10.5 mg/dL or 2.6 mmol/L, with/without elevated serum intact PTH > 65 pg/ml or 6.9 pmol/L) persists at or after the 6th postoperative month. [Time Frame: 6 months after PTx procedure]

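### Section 6 claims 95% power for 33 patients per group, but its stated inputs give about 80%; the figure concerns secondary outcome 2.3.1, and no primary outcome has a power statement

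*Combined protocol and SAP*

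**What the plan says.** Section 6 (Statistical Considerations) holds the protocol's only sample-size calculation. It starts from a study of NIRAF imaging that reported 3.1 ± 0.9 glands identified in 93 patients with imaging and 2.6 ± 0.1 in 153 without. Section 6 summarises this as a difference of 0.5 with SD 1.0. It then plans on a difference of 0.7 with SD 1.0 and concludes that "33 patients would be required per group (for a 95% powered study"). Alpha, sidedness and the test are not given.

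The 33 is raised to 40 per group for 20% attrition, because the study may involve "patient follow-up for data up to 6 months after surgery". The result is stated for each surgeon: "a total of 80 patients (study and control arm) should be recruited per surgeon". The Protocol Summary gives N = 160, with 40 + 40 per investigator.

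The number of glands identified is secondary outcome 2.3.1, and its entry ends: "Control Group: Glands identified with naked eye) [Time Frame: Immediate. During PTx procedure". The primary outcomes are binary and different in kind:

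- 2.2.1: "Failure of intra-operative parathyroid hormone (PTH) to normalize"
- 2.2.2: raised calcium, with or without raised PTH, at the first postoperative visit
- 2.2.3: "Patient is defined to have a failed parathyroidectomy if hypercalcemia/hyperparathyroidism" persists at or after the sixth month

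None of the three has an assumed rate, a detectable effect or a power figure.

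**The concern.** The one power figure in the protocol does not follow from the numbers printed beside it. Anyone reading a single surgeon's results would believe the gland-count comparison more sensitive than it is.

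The figure is also easy to carry over to the wrong outcome. Section 3.1 gives the primary outcome the job of evaluating the efficacy of PTeye, yet the calculation is for a secondary one. Section 6 calls the study as a whole 95% powered and does not say that this leaves out 2.2.1 to 2.2.3. The attrition argument adds to the confusion: it rests on 6-month follow-up, which matters for 2.2.3 but not for a count made in the operating room.

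**Working it through.** **Inputs.** From Section 6: planned difference 0.7, SD 1.0; difference attributed to the cited study 0.5, SD 1.0; n = 33 per group at a claimed 95%; 40 per group after the attrition allowance (33 × 1.2 = 39.6). From the Protocol Summary: 160 / 80 = 2 surgeons. Assumed, because the protocol does not say: two-sample t-test at two-sided 5%, with one-sided 5% as a check.

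**Step 1: reproduce the 33.** Normal formula, n per group = 2 × SD² × (z for alpha + z for power)² / difference²:

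- 80% power: 2 × (1.9600 + 0.8416)² / 0.7² = 2 × 7.849 / 0.49 = 32.04, so 33.
- 95% power: 2 × (1.9600 + 1.6449)² / 0.7² = 2 × 12.995 / 0.49 = 53.04, so 54.

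The t-test solutions are 33.02 and 54.02, so 95% needs 55 per group. The printed 33 is what an 80% calculation gives.

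**Step 2: power at 33 per group.** The standardised signal is 0.7 × √(33/2) = 2.843. The normal approximation gives Φ(2.843 − 1.960) = Φ(0.883), about 81%; the t-test gives 80.0%. At one-sided 5% the t-test gives 87.9%, and 95% needs 45 per group. With 0.7 and 1.0 held fixed, 95% at 33 would need a two-sided alpha of about 0.24.

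**Step 3: power at the sizes that matter** (t-test, two-sided 5%, SD 1.0):

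| Per group | Setting | Difference 0.7 | Difference 0.5 |
|---|---|---|---|
| 33 | one surgeon, as calculated | 80.0% | 51.6% |
| 40 | one surgeon, as enrolled | 87.1% | 59.8% |
| 80 | two surgeons pooled, as enrolled | 99.3% | 88.2% |

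The 40 and 80 rows take no loss, because glands are counted during the operation.

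**Step 4: could other inputs lie behind the figure?** Pooling the SDs reported from the cited study: √[(92 × 0.9² + 152 × 0.1²) / 244] = √0.3116 = 0.558. With difference 0.5 the normal formula gives 2 × 0.3116 × 12.995 / 0.25 = 32.4, so 33 at 95% (t-test power at 33: 94.8%). This reproduces the pair 33 and 95%, but with neither the difference nor the SD that Section 6 ties to it.

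**The case against.** Four points can be made for the plan.

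- **The 95% may not be the wrong number.** Step 4 shows that 33 and 95% agree for a difference of 0.5 and SD 0.56, so the slip could lie in the stated difference and SD. This stands as far as the remedy goes: the authors must be free to correct whichever element is wrong. It does not rescue the sentence, which names 0.7 and 1.0.
- **N = 160 is not short for gland count.** With two surgeons pooled, power is about 99% for 0.7 and 88% for 0.5. This stands, subject to the protocol not saying whether surgeons are pooled; Section 6 speaks per surgeon.
- **Gland count is not a stray endpoint.** Identification of parathyroid tissue is item (i) of the primary objective in Section 2.1, so sizing on it follows a stated aim. This stands, but Section 2.3.1 still lists the count as secondary and Section 2.2 names three other outcomes as primary.
- **The 95% directly follows the gland-count figures, and no text applies it to the primary outcomes.** True. The misreading is a risk that one sentence would remove; the protocol does not itself make the error.

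A reader might go further and infer that the trial is shown to be underpowered for its primary outcomes. The documents do not support a figure for that. They state no control rate or effect for 2.2.1 to 2.2.3. The 5–10% "of cases resulting in failed parathyroidectomies" in Section 1 is a general background figure for failure to find the diseased gland, not a planning rate for 2.2.3 as defined. If it is nevertheless taken as the control rate, with surgeons pooled, 80 per arm and a two-sided 5% Fisher test, power depends almost wholly on the assumed effect: 4% for 5% vs 2.5%, 14% for 10% vs 5%, 21% for 5% vs 0 and 82% for 10% vs 0.

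**Conclusion.** The concern holds as an error in the stated power and an omission, not as a shortfall in patient numbers. On Section 6's own difference and SD, the power for one surgeon at 33 per group is about 80%, roughly 15 percentage points below the claim, and the sample size for 95% is 55 rather than 33. This rests on a two-sided 5% test; one-sided 5% narrows the gap to about 7 points and does not close it. The calculation applies to 2.3.1 alone, and its attrition allowance is justified by follow-up that this outcome does not need. That 2.2.1 to 2.2.3 have no power statement is a matter of reading and needs no assumption. Neither a claim that 160 patients are too few for gland count nor a specific low power for a primary outcome follows from the documents.

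**What to change.** Keep N = 160 and the outcome hierarchy, and rewrite the Section 6 paragraph by amendment:

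1. Restate the power for 33 per group per surgeon as about 80% at difference 0.7, SD 1.0, two-sided 5%, and about 87% at the 40 per group enrolled. If other inputs were really used, correct the stated difference and SD instead, so that n, power, difference and SD agree.
2. State alpha and sidedness, and say whether the surgeons are pooled. If they are, give gland-count power at 80 per arm: about 99% for 0.7 and 88% for 0.5. Note that the count is made during surgery and is not exposed to 6-month loss.
3. State that the calculation applies to 2.3.1 only, that the trial was not sized for 2.2.1 to 2.2.3, and that the power figure does not extend to them. A power figure for 2.2.3 is optional; if given, label it as resting on an assumed control rate and effect.

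The cost is one paragraph and its approval, with no added patients, visits or procedures.

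### Recruiting 40 per group leaves 32, not the required 33, at exactly the plan's 20% attrition; the effect is small and the text can be corrected without enrolling more patients

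*Combined protocol and SAP*

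**What the plan says.** Section 6 sizes the trial on the mean number of parathyroid glands identified, with "expected mean difference: 0.7 and expected standard deviation: 1.0". From this it concludes that "33 patients would be required per group (for a 95% powered study". It then cites follow-up of up to 6 months as the reason for an allowance for lost data: "we will thus assume an approximate data attrition rate of 20%, thus requiring a recruitment of 40 patients per group". The 40 per group becomes 80 per surgeon. The Protocol Summary carries the same figure: "Each investigator will enroll 40 subjects to the PTeye group and 40 subjects to the control group", with N = 160.

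No inflation formula, alpha level or sidedness is given. Section 2.3.1 lists the overall number of glands identified as a secondary outcome, recorded during the procedure. The outcomes that need follow-up are the primary outcomes in Section 2.2.2 (5 to 14 days) and Section 2.2.3 (6 months), together with some later secondary outcomes.

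**The concern.** The plan presents 40 as the number that follows from a need for 33 and a 20% loss. Anyone who multiplies 40 by 0.8 gets 32, so the stated size does not meet the plan's own requirement at its own rate. Every recruitment figure in the protocol (40, 80 and 160) rests on this step. At stake is whether the sample size statement is internally consistent and whether the power quoted beside it describes the patients expected to remain for analysis.

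**Working it through.** **Inputs.** From Section 6: 33 per group required, 20% attrition (called approximate), 40 per group recruited, difference 0.7, SD 1.0, stated power 95%. From the Protocol Summary: 40 + 40 per investigator, N = 160. Assumed, because not stated: two-sided alpha of 5%. The power figures are for one surgeon's two groups, the unit that Section 6 uses.

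**1. Reproducing the 40.**
- Multiplying up: 33 × (1 + 0.20) = 39.6, rounded to 40. This matches the plan.
- Dividing by the retained fraction: 33 / (1 − 0.20) = 41.25, rounded up to 42. This does not match.

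The first route is an inference about how 40 was reached. The next step does not depend on it.

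**2. What 40 delivers.**
- At exactly 20% loss: 40 × 0.8 = 32, one below 33.
- Largest loss that still leaves 33: 1 − 33/40 = 17.5%.
- If each patient independently has a 20% chance of loss, a group of 40 keeps at least 33 with probability 0.44; a group of 42 does so with probability 0.68.

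**3. Power** (two-sample t-test, difference 0.7, SD 1.0, two-sided 5%).

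| Evaluable per group | Power |
|---|---|
| 32 | 78.7% |
| 33 | 80.0% |
| 40 | 87.1% |
| 42 | 88.7% |

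The missing patient costs 80.0 − 78.7 = 1.3 points.

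**4. The base of 33.** The normal approximation is n = 2 (z for alpha + z for power)² × SD² / difference².
- 80% power: 2 × (1.960 + 0.842)² / 0.49 = 32.04, so 33. This reproduces the plan's number.
- 95% power: 2 × (1.960 + 1.645)² / 0.49 = 53.04, so 54. The t-test solution is 54.02, strictly 55.
- One-sided 5% does not rescue the 95% claim: it needs 45 per group.

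So 33 is the size for about 80% power, not 95%.

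**5. Consistent recruitment figures if 33 is accepted as the base.** 42 per group, 84 per surgeon, and 168 for the two surgeons implied by 160 / 80. From a base of 54, dividing gives 54 / 0.8 = 67.5, so 68, while multiplying gives 54 × 1.2 = 64.8, so 65. The inflation method therefore matters more if the base is ever recalculated.

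**The case against.** Four points can be made for the plan.

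- **The rate is approximate.** Section 6 says so, and 40 does leave 33 if the loss is 17.5%. A reader might infer that 40 per group cannot yield 33 evaluable patients. The documents do not support that; the shortfall arises at exactly 20%. But the plan presents 40 as derived from 20%, and that derivation does not close.
- **The mechanism is not shown.** A reader might take multiplication by 1.2 as established. It fits exactly, but 41.25 could also have been rounded down to a convenient number. Only the comparison of 32 with 33 can be demonstrated from the text.
- **The sizing endpoint is intraoperative.** A patient lost by 6 months still has a gland count, so nearly all 40 may be evaluable for it, with about 87% power. This stands, and it means the shortfall is unlikely to appear in the analysis that was sized. The outcomes that are exposed to follow-up loss were not used to derive 33. The plan nevertheless applied the allowance to this number, so the text should either apply it consistently or say what it is for.
- **The 95% power statement is the larger error in the same paragraph.** This also stands. Moving from 40 to 42 would not touch it. It does not make the attrition step right, and both can be corrected together.

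**Conclusion.** The sample size statement is wrong as written, with a minor practical effect. At exactly 20% attrition, 40 per group leaves 32 evaluable, one short of 33, and the consistent figure would be 42. The cost is about 1.3 points of power at a difference of 0.7 and SD 1.0, assuming a two-sided 5% test within one surgeon's groups. For the gland count the cost is likely to be smaller or nil, because follow-up loss hardly affects it.

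A reader might infer that the trial must enrol 42, 84 and 168. That does not follow. Those figures are right only if 33 is accepted as the required number, and 33 does not deliver the power that the plan attaches to it. What needs to change is the text, not the enrolment target.

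**What to change.** Keep 40 per group, 80 per surgeon and 160 in total, in both Section 6 and the Protocol Summary, and rewrite the end of the Section 6 paragraph:

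1. State either that 40 per group leaves 32 evaluable after 20% attrition, or that 40 per group allows for 17.5% attrition and still leaves 33.
2. Say that the allowance is meant for the outcomes that need follow-up, and that the gland count, being recorded during surgery, is expected to be available for nearly all patients.
3. Replace the 95% power statement and give the alpha and sidedness used. For a two-sided 5% test at 0.7 and SD 1.0, power is about 80% with 33 per group, about 79% with 32 and about 87% with all 40 evaluable.

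The cost is a few lines in Section 6, with no change to recruitment or procedures. The stated power becomes less favourable.
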